#### 20.3.4 Safety Analyses

Means and standard deviations of plasma CBD and THC levels within the CBD treatment group will be presented following 45 minutes (T1), 1 day (T2), 1 week (T3), 2 weeks (T4), 4 weeks (T6),6 weeks (T8) of treatment with CBD vs. placebo, and one week (T9) after the completion of treatment to determine whether target plasma levels of CBD have been achieved, and whether metabolic transformation of CBD to THC has occurred.

The number of participants within each treatment group that were able to pass a battery of psychomotor field sobriety tasks (walk-and-turn task, one-leg stand, Romberg's test, finger-finger test, and counting backwards

[85]) within 2 hours of the initial administration of CBD vs. placebo (T1) will be analyzed as summary statistics during treatment.

AEs and SAEs, when present, will be collected on an AE Case Report Form at study visits. The form will include an assessment of clinical significance and study relatedness. Serious Adverse Events (SAEs) will be documented on an additional SAE form. These CRFs will be based on those used in recent NIDA Clinical Trials Network trials. To further assess abuse potential, visual analog scales will be used to assess abuse potential. Scales will include desire to use the study medication again, desire to use the study medication again for pleasurable intoxication ("to get high"), and craving for the study medication.

The study may be stopped if there are untoward and concerning levels of Adverse Event (AE) or Serious Adverse Event (SAE) outcomes attributable to CBD or study participation. If the DSMB finds it is likely that CBD is contributing to negative outcomes, they will consider solutions including protocol changes or potentially stopping the study.

The frequency of adverse events will be analyzed for the entire sample tabulated for each treatment group and compared using chi-squared tests. The safety analysis will be largely descriptive of outcomes for the entire study population. The incidence of AEs will be summarized by system organ class, preferred term, the likelihood of its relationship to the treatment, and severity for each treatment group. Clinical laboratory data will be summarized by type of test. Frequency and percentage of patients whose values fall outside of reference ranges will be presented for each measurement.

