## 6.3.1 Administration of Intervention

CBD (or placebo) will be administered daily for 6 weeks. The first administration of CBD vs. placebo (at T1) will take place at the study site. Participants will remain at the study site with a study team member for approximately 2 hours following the initial administration of each dose of CBD, and participants will not be permitted to leave the study site until they are able to pass a standard field sobriety test (a walk-and-turn task, one-leg stand, Romberg's test, finger-finger test, and counting backwards [85]). If there are no AEs during this time-period or lasting intoxicating effects of the study drug (i.e. participants are able to pass field sobriety tests 2-3 hours after study drug administration), participants will be given a 1- or 2-week supply of the study drug (CBD or placebo) to self-administer daily at home until the next scheduled study visit.

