#### 45 minutes +/- 10 minutes (T1)

- Collect blood and plasma for CBD, THC, and AEA levels at 45 minutes post medication (post-CBD levels)
- Record adverse events as reported by participant or observed by investigator
- · Results of evaluations of safety, and psychomotor effects
- Record participant's adherence to treatment program

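### The psychomotor safety count does not say which attempt at the battery is scored, and its 2-hour cut-off does not match the leaving check at 2-3 hours

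*Combined protocol and SAP*

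**What the plan says.** Section 20.3.4 (Safety Analyses) gives the only stated analysis of the field sobriety battery. The quantity is "The number of participants within each treatment group that were able to pass a battery of psychomotor field sobriety tasks", and the timing is "within 2 hours of the initial administration of CBD vs. placebo (T1) will be analyzed as summary statistics during treatment". The sentence does not give the minute of assessment, the number of attempts allowed or the attempt that is scored. It specifies no test.

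Section 6.3.1 applies the same five tasks for a different purpose. On length of stay: "Participants will remain at the study site with a study team member for approximately 2 hours". On leaving: "participants will not be permitted to leave the study site until they are able to pass a standard field sobriety test". Take-home supply then depends on whether "participants are able to pass field sobriety tests 2-3 hours after study drug administration".

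The T1 visit in Section 7.3.3, set at 45 ± 10 minutes, lists "Results of evaluations of safety, and psychomotor effects". It does not name the battery, but Section 7.1.4 describes psychomotor evaluation mainly through these five tasks. Section 7.3.2 lists a psychomotor evaluation at B1, ahead of the item on giving the dose.

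The Protocol Summary lists scores on psychomotor tasks among the primary endpoints. Section 3.1 predicts psychomotor side effects no greater than on placebo, and Hypothesis 1a in Section 20.2 predicts no clinically significant motor impairment.

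**The concern.** One battery serves two purposes. As a safety measure, it should describe a participant's state at a fixed time after dosing. As a leaving check, it is repeated until passed. A count of those who managed to pass by a deadline mixes the drug effect with the moment at which staff chose to retest. A transient early impairment can then be tabulated as no impairment.

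This matters because psychomotor safety belongs to the primary objective, and Section 20.3.8 says that the primary outcomes are safety data for which no difference between arms is hypothesised. An insensitive measure can favour that hypothesis. The analysis of Hypothesis 1a in Section 20.3.2 covers adverse events and laboratory data only, so no second planned analysis of the battery would make up for it.

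**Working it through.** The plan gives no failure rate or power figure for this item, so there is nothing to reproduce. The check compares time windows and then shows the possible range.

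**Windows after the first dose**
- T1 evaluation (Section 7.3.3): 45 ± 10 minutes, that is 35 to 55 minutes.
- Analysis window (Section 20.3.4): 0 to 120 minutes.
- Check before take-home supply (Section 6.3.1): 2-3 hours, that is 120 to 180 minutes.

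The analysis window and the Section 6.3.1 check meet only at 120 minutes. No attempt is scheduled between 55 and 120 minutes, and none is ruled out.

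**Literal scoring of three hypothetical participants**
- Passes at 45 minutes: counted as a pass.
- Fails at 45 minutes, passes a repeat at 1 h 55: counted as a pass.
- Fails at 45 minutes, passes at 2 h 05: not counted as a pass.

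The first two differ at 45 minutes but score the same. The last two have the same 45-minute result and nearly the same recovery, but score opposite ways.

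**Range of the effect on the count**
Let f be the proportion of CBD participants failing at 45 minutes and r the share of those who pass a repeat by 2 hours. Neither is in the documents. I assume f from 10% to 40% and r from 0 to 100%. With 30 on CBD (Section 20.5.1), expected failures are 30 × f at the first attempt and 30 × f × (1 − r) under the planned count.

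| f | First attempt | Planned count, r = 0 | r = 50% | r = 100% |
|---|---|---|---|---|
| 10% | 3 | 3 | 1.5 | 0 |
| 20% | 6 | 6 | 3 | 0 |
| 30% | 9 | 9 | 4.5 | 0 |
| 40% | 12 | 12 | 6 | 0 |

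The r = 0 column also covers the case in which the only repeat comes after 2 hours.

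**What a clean result would show**
With no failures among n participants, the upper end of the exact two-sided 95% interval is 1 − 0.025^(1/n). This gives 11.6% for 0/30 and 18.5% for 0/18. Even a full set of passes would leave sizeable failure rates open, so the count should at least refer to a defined time.

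**The case against.** The strongest objection is that the masking needs an event the documents do not schedule: a repeat between 55 and 120 minutes. The only later check with a stated time is at 2-3 hours. If that is when the repeat happens, a 45-minute failure remains a non-pass and stays visible. This stands, and it is why the effect may be nil.

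A reader might go further and infer that the leaving rule drives pass rates towards 100% in both arms, so that the no-difference prediction is bound to be met. The documents do not support that. The leaving rule has no time limit whereas the count stops at 2 hours, so passes obtained under the rule may fall outside the count. Omitting a pass at 2-3 hours does not hide impairment either; that part is a mismatch of windows. Nor can a loss of power be claimed: no failure rates are given, and Section 20.3.4 plans summary statistics without a test for this item.

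Other routes to detection exist. Adverse events are collected with SAFTEE and compared by arm, the ARCI measures intoxicating effects, and psychomotor results are recorded at later visits. These reduce what is at stake but do not define the battery endpoint. Section 20.1 defers a formal SAP to before database lock and unblinding, which is an opportunity to settle the point rather than an answer to it.

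Finally, scoring T1 alone would miss someone who passes at 45 minutes and is impaired at 90. That is correct, and the fix therefore keeps the later attempts.

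**Conclusion.** The point holds as a gap in the endpoint definition. The planned count depends on an unstated attempt rule and on when staff retest, and its 2-hour cut-off does not match the check in Section 6.3.1. It also reduces an endpoint described as scores to a pass count.

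Masking of early impairment is permitted by the wording but is not certain. Its size runs from none to complete and cannot be narrowed from the documents. The conclusion assumes that the T1 psychomotor evaluation includes the five-task battery, which Section 7.1.4 suggests but the T1 list does not say. That the B1 evaluation precedes dosing is likewise inferred from the order of the visit list. The change is worth making because the measure serves a primary safety prediction and the evaluations are already scheduled.

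**What to change.** In Section 20.3.4 and the formal SAP:

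1. State that the T1 psychomotor evaluation is the five-task battery, and make the first post-dose attempt at 45 ± 10 minutes the scored result: pass or fail, and number of tasks failed.
2. Present it by arm alongside the same participants' B1 result, with the difference between arms and a 95% interval. State in the schedule that the B1 battery precedes dosing.
3. Report every later attempt by its clock time, including the leaving check, and summarise time to pass, so that impairment arising after 45 minutes is also seen.
4. Reconcile the 2-hour window in Section 20.3.4 with the 2-3 hours in Section 6.3.1, and the pass count with the scores named in the Protocol Summary.

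The cost is revised wording, a test-time field on the form and one more table. No change to the leaving rule is proposed.

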# **Protocol Summary**

Title	A Phase I/II Randomized, Double-Blind, Placebo-Controlled Trial of Cannabidiol for Alcohol Use Disorder comorbid with Post Traumatic Stress Disorder
Brief Summary	The proposed study is a double-blind, randomized proof-of-concept study designed to assess feasibility and contrast effects of CBD treatment to those of placebo on safety, drinking-related outcomes and PTSD related outcomes in patients with AUD+PTSD. We will evaluate the safety of an extended daily CBD treatment regimen in an AUD+PTSD population, measure resulting CBD, THC, and anandamide levels, and generate preliminary data on the impact of CBD on alcohol use, PTSD symptoms, and neuropsychological and neurophysiological domains implicated in AUD and PTSD. 150 participants will be enrolled to randomize 48 eligible participants who fully meet study criteria in a 5:3 ratio to receive either 600mg CBD/day (PO) or placebo respectively for 6 weeks (N=30 participants on CBD and N=18 participants on placebo). Clinical interviews or portions of the interview will be audio taped to ensure quality control. Deidentified audio recordings of participants who consent to participate in the voice-markers analysis will be encrypted and sent via secure sites for analysis to a HIPAA compliant specialized labs.
Phase	Clinical study phase I/II
Objectives	To assess the safety and feasibility of administering CBD in an AUD+PTSD population; to generate preliminary data on the effect of CBD in reducing self-reported measures of alcohol use and PTSD symptoms and the impact of CBD upon neurophysiological and neuropsychological domains relevant to AUD+PTSD; to assess plasma for CBD, THC and anandamide levels.
Methodology	Double-blind, placebo-controlled
Endpoint	Primary endpoints: Adverse events and scores on psychomotor and cognitive tasks, number of drinks per day and PCL-5 total score. Secondary endpoints: circulating concentrations of CBD, THC and anandamide.
Study Duration	2 years
Participant Duration	9 weeks
Duration of IP administration	6 weeks
Population	n=48 (randomized) 18–70 year-old males and females with moderate to severe AUD, as well as a DSM diagnosis of either PTSD or subthreshold PTSD in the New York area.
Study Sites	New York University Grossman School of Medicine
Number of participants	150 participants expected to be enrolled, 48 participants expected to be randomized
Description of Study Agent/Procedure	Cannabidiol PO 600mg/day

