# **3 Objectives and Purpose**

## 3.1 Primary Objective

The primary objective is to obtain a preliminary assessment of the safety, tolerability, efficacy, and effect size of CBD in reducing self-reported measures of alcohol use and PTSD symptoms in the AUD+PTSD/subthreshold PTSD population.

We predict that treatment with 600mg CBD daily will be well tolerated with no greater psychomotor or other motor side effects compared to treatment with placebo. We predict that CBD will be associated with a greater reduction in drinks per day and PTSD symptoms (total PCL-5 score) compared to placebo.

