## Psychomotor and subjective effects of CBD

Basic motoric and cognitive function will be evaluated throughout treatment with several established field sobriety tests, including a walk-and-turn task, one-leg stand, Romberg's test, finger-finger test, and counting backwards [85]. The Addiction Resource Center Inventory (ARCI), 49-item version [86], will be used as a measure of the intoxicating effects and abuse potential of CBD. Breath Alcohol Concentration (BAC) will also be measured to ensure participants are not under the influence of alcohol during administration of these tasks.

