## 20.2 Statistical Hypotheses

Hypothesis 1a Safety and tolerability: CBD will be safe and well tolerated and will not lead to increased plasma THC. No clinically significant cognitive or motoric impairments, CBD-related serious adverse events, persisting adverse effects or treatment associated increases in plasma THC will be observed.

Hypothesis 1b: Alcohol use. Relative to the placebo-treated group, CBD-treated participants will have fewer drinks per day during the 6 weeks of treatment with CBD vs placebo.

Hypothesis 2: PTSD symptoms. Relative to the placebo-treated group, CBD-treated participants will lower PTSD symptoms during the 6 weeks of treatment with CBD vsplacebo.

Hypothesis 3a: Mechanism, traumatic stress-induced craving: Relative to placebo, CBD will be associated with a greater reduction between baseline and end of treatment in trauma induced alcohol craving, negative emotion, and psychophysiological arousal in response to the task.

Hypothesis 3b: Mechanism, AUD and PTSD related measures and cognition: Relative to placebo, CBD will improve self-report measures of craving, anxiety, mood, self-efficacy and cognitive performance.

Hypothesis 3c: Mechanism, anandamide: Relative to placebo, CBD will be associated with a greater increase

Hypothesis 4: CBD plasma levels. Within-group plasma CBD levels will stabilize within one week, i.e. 45 minutes post-CBD dosing levels obtained after 1 week of treatment will not differ from those obtained after 4 weeks of treatment at each dose.

Exploratory Hypothesis 1: Relationship between effects on PTSD symptoms and alcohol use. The onset of reduction in PTSD symptoms will precede the onset of reduction in alcohol use.

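### The field sobriety battery has a stated analysis only at the first dose (T1); five of its six on-treatment assessments, including all those at expected steady state, have none

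*Combined protocol and SAP*

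**What the plan says.** Section 3.1 makes psychomotor tolerability under daily treatment part of the primary objective: "We predict that treatment with 600mg CBD daily will be well tolerated with no greater psychomotor or other motor side effects" than placebo. Hypothesis 1a in section 20.2 predicts "No clinically significant cognitive or motoric impairments" and does not limit this to the first dose. The Protocol Summary names as primary endpoints "Adverse events and scores on psychomotor and cognitive tasks", together with the drinking and PCL-5 outcomes. Section 4.2.1 is narrower: it defines primary safety through adverse events and liver function tests.

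On collection, the paragraph on psychomotor and subjective effects in section 4.2.2, repeated in 7.1.4, says: "Basic motoric and cognitive function will be evaluated throughout treatment with several established field sobriety tests". The visit lists in 7.3 include psychomotor evaluation at baseline and at T1, T2, T3, T4, T6, T8 and T9.

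On analysis, section 20.3.4 counts the participants in each arm who pass the battery "within 2 hours of the initial administration of CBD vs. placebo (T1) will be analyzed as summary statistics"; the sentence then ends with a reference to the treatment period. No other analysis of these tests is given.

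**The concern.** The prediction is comparative and concerns six weeks of daily treatment. The stated analysis is a count per arm after one dose. That reading precedes the steady state which the dose rationale expects within a week, so it cannot show whether impairment builds up with repeated dosing. The later tests are scheduled and will be in the database, but nothing says how, or whether, they will be reported. Motor impairment seen on testing at weeks 1 to 6 could therefore be recorded and never appear in the results, or its presentation could be chosen after the data are seen.

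**Working it through.** No figure in the plan bears on this point: it gives no failure rate, margin or power for the psychomotor tests. The check is a count of scheduled assessments against stated analyses.

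**1. Scheduled assessments (section 7.3)**

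| Time point | Psychomotor evaluation listed | Analysis of the battery stated |
|---|---|---|
| B1 (before treatment) | yes | no |
| T1 (45 minutes after first dose) | yes | yes, 20.3.4 |
| T2 (day 1) | yes | no |
| T3 (week 1) | yes | no |
| T4 (week 2) | yes | no |
| T5, T7 (phone calls) | no | not applicable |
| T6 (week 4) | yes | no |
| T8 (week 6) | yes | no |
| T9 (week 7, after treatment) | yes | no |

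On treatment there are 6 assessments: T1, T2, T3, T4, T6, T8. One has a stated analysis, so 6 − 1 = 5 do not. Four of those five (T3, T4, T6, T8) are scheduled at or after the one week by which steady state is expected.

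**2. In person-assessments, assuming full attendance.** With 30 on CBD and 18 on placebo:
- Scheduled on treatment: 30 × 6 = 180 on CBD and 18 × 6 = 108 on placebo, 288 in all.
- With a stated analysis: 30 + 18 = 48.
- Without: 288 − 48 = 240.

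**3. Position of the analysed reading.** Section 6.1.5 gives two administrations a day for six weeks, 2 × 42 = 84. The T1 reading follows the first of these.

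**4. Search of the other analysis sections**
- 20.3.2, hypothesis 1a: adverse events and laboratory values. The battery is not mentioned.
- 20.3.3, hypothesis 3b: craving, self-efficacy, anxiety and cognitive measures, with a week 6 contrast. The motor tests are not listed.
- 20.3.4: the T1 count only. The same section lists T1, T2, T3, T4, T6, T8 and T9 one by one for plasma CBD and THC, so the authors name visits where they intend a by-visit summary.

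**5. What a later between-arm comparison could show.** As an illustration, assume a 5% failure rate on placebo, a figure not in the documents. Power of a two-sided Fisher exact test at 0.05 is the sum, over all possible tables with p ≤ 0.05, of Bin(x; 30, p1) × Bin(y; 18, 0.05). This gives 0.18, 0.52 and 0.81 for CBD failure rates p1 of 20%, 30% and 40%. An estimate with its interval is therefore more useful than a test.

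**The case against.** **The sentence in 20.3.4 ends with a reference to the treatment period.** This stands as an ambiguity. Those words fit poorly with a count fixed at T1, and the authors may have meant more. But they name no later visit, score or comparison, so they do not define an analysis of the later tests.

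**Adverse events already cover motor side effects.** This largely stands and limits the point. Adverse events are collected with SAFTEE after treatment starts, analysed at all time points and compared between arms by chi-squared test (20.3.2, 20.3.4). A reader might infer that the whole psychomotor safety question rests on one first-dose reading, or that impairment under repeated dosing goes unanalysed. The documents do not support that. What remains is impairment seen on testing but not recorded as an adverse event; nothing in the plan requires a failed test to be recorded as one.

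**The battery is not clearly primary.** True in part. Section 4.2.1 and the Protocol Summary differ, and the tests are described under 4.2.2. The prediction in 3.1 still concerns psychomotor effects under daily treatment.

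**The count is inferred.** The later visit lists refer to psychomotor/subjective effects without naming the battery, and that heading also covers the ARCI. Sections 4.2.2 and 7.1.4 supply the link. T9 falls after treatment and is left out of the six.

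**The time limits differ.** Section 6.3.1 speaks of whether "participants are able to pass field sobriety tests 2-3 hours after study drug administration", while 20.3.4 uses 2 hours. A reader might call this an error. It need not be: the first is a condition for leaving the site and the second an outcome cut-off, and someone who first passes at 2.5 hours is correctly counted as not passing within 2 hours. Because participants stay until they pass, an outcome defined by release would drift toward a ceiling.

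**A formal SAP is still to come (20.1).** It may fill the gap, but nothing in these documents does so yet.

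**Conclusion.** The gap is real but bounded. Five of six on-treatment psychomotor assessments, up to 240 of 288 scheduled person-assessments, have no stated analysis, and these include all four at expected steady state. The one reading that is analysed cannot address repeated dosing. The consequence is confined to test-detected impairment that does not reach the adverse event record.

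This rests on three assumptions: that the visit lists mean the field sobriety battery when they refer to psychomotor effects; that the closing words of the 20.3.4 sentence do not stand for an unstated by-visit analysis; and that attendance is complete, which makes 288 a maximum. The change should be made before database lock and unblinding. It does not undermine the trial.

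**What to change.** In section 20.3.4:

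- Keep the T1 count, and clarify or remove the closing reference to the treatment period.
- Add pass/fail for the battery by arm at T2, T3, T4, T6 and T8, with T9 shown separately as off-treatment follow-up.
- Give the number tested at each visit. Section 7.3.3 lets intermediate visits without safety labs be remote, and T2, T3 and T6 list no liver function tests, so results there may be missing.
- Report the between-arm risk difference with a two-sided 95% CI at T8 and for any failure from T3 to T8, stating for the latter how many of the four tests each participant completed.
- Include all tests in the main table, and add a sensitivity table without tests taken at a positive breath alcohol. Excluding those tests from the main table would condition on drinking after randomisation, which hypothesis 1b expects CBD to change.
- State that the 2-hour limit is an outcome definition distinct from the release check in 6.3.1, or reconcile the two passages.

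The cost is SAP wording and a small amount of extra tabulation. No new visit, test or participant is needed; some visit-level missing data must be accepted and shown.
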